6.4 End of Trial Definition

A patient will be considered as having completed the trial when:

- Patient completed EOT visit and exit interview, if consented (Danish, French, German, UK and US, sites only) and will continue participation in Extension Trial.
- Patient completed Follow-up (FU)/Final Visit and exit interview, if consented (Danish, French, German, UK, and US, sites only) and will not enter the Extension Trial.

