10.4.10 Visit 10 (End of Treatment; Week 24/Day 169 ± 7 days)

During Visit 10, the following assessments will be performed:

- Complete PROs (PGIC, SBS-I, and EQ-5D-5L)
- Record any procedures and changes to concomitant medications
- Perform 12-lead ECG
- Record body weight

- Record vital signs (heart rate, systolic and diastolic blood pressure, and body temperature)
- Record AEs
- Perform short physical examination (driven by SBS symptoms)
- Collect urine sample for urinalysis
- Obtain blood samples for:
 - hCG pregnancy test (for females of childbearing potential only)
 - Hematology
 - Biochemistry
 - Citrulline (drawn prior to dosing, if dosing on the same day)
 - PK (drawn prior to dosing, if dosing on the same day)
 - ADA (drawn prior to dosing, if dosing on the same day)
 - Bone markers
- Review eDiary information for:
 - PS use
 - Trial product administration (including injection site, time of administration)
 - 48-hour oral fluid intake
 - 48-hour urine volume
 - 48-hour bowel movements/stoma bag emptying
- Record adherence to PS regimen (including weekly schedule, volume, and content) and modify weekly PS volume and schedule in accordance with [Section 8.7.3](#)
- Patient to return all used and unused vials and dispensing cartons. Account for returned trial product
- Decision whether the patient will participate in the Extension Trial or not
 - If not participating
 - The patient should resume standard of care and the treating physician is advised to pay careful attention to the PS regimen
 - The patient should attend the Follow-up/Final visit
 - If the patient agrees to enter the Extension Trial:
 - Complete the end-of-trial form in the eCRF
 - Exit Interview (selected countries only)
 - The exit interviews, if consented (Danish, French, German, UK and US sites only sites only) will be conducted no longer than 7 days after EOT visit

- Investigator to review the transcript of exit interview for potential AE reporting within 2 days after receiving the transcript.

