12.1 General Considerations for Data Analysis

This is a multicenter, placebo-controlled, randomized, parallel-group, double-blind, fixed-dose, Phase 3 trial to demonstrate the superiority of glepaglutide 10 mg given twice weekly and once weekly SC versus placebo in stable SBS patients.

A detailed Statistical Analysis Plan (SAP) will be written specifying all analyses that will be performed and completed prior to database lock and analysis. The SAP will contain any modifications to the analysis plan described below, and thus serves as the overriding document dictating the statistical analyses to be performed. Any changes from the SAP will be explained in the Clinical Trial Report (CTR).

In general, all data will be summarized with descriptive statistics for each treatment group. Unless otherwise specified, continuous data will be summarized by presenting the number of

non-missing observations, mean, standard deviation (SD), median, minimum, and maximum. Categorical data will be summarized by presenting the number of patients and percentage for each category.

Baseline is defined as Visit 1 (Day 1) for efficacy analyses, and defined as the last available value prior to or on Visit 1 (Day 1) for safety analyses.

Inferential statistical analyses of the primary and secondary efficacy endpoints will be performed as described below. All comparisons will be between each ZP1848-17111 treatment group and placebo. Listings of individual patient data will be presented.

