12.4 Safety Analysis

Safety endpoints are:

- Incidence and type of AEs and SAEs
- Change in clinical evaluations:
 - Vital signs
 - ECG
- Change in laboratory assessments:
 - Hematology
 - Biochemistry
 - Urinalysis
 - Standard bone markers

- Immunogenicity

All safety analyses will be conducted using the Safety Analysis Set. No inferential tests of safety data will be performed. Descriptive summaries of safety data will be presented and for each AESI, a time to event analysis will be performed. This will be detailed in the SAP. Adverse events (treatment-emergent unless otherwise specified) will be presented by system organ class (SOC) and preferred term (PT) for each treatment group.

Treatment-emergent AEs are defined as AEs with onset date on or after the first day of exposure to randomized treatment up through the last day prior to the start day of the Extension Trial or to the Week 28 (for patients not entering the Extension Trial).

Immunogenicity endpoints will be associated with PK, efficacy, and safety endpoints as appropriate and described in detail in the SAP.

Standard bone markers will be assessed as an exploratory endpoint.

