7.1. EXPOSURE AND TREATMENT INTERRUPTIONS

It should be noted that according to the protocols, the investigator can decide to pause treatment with the investigational product if a patient experiences an AE that is considered related to investigational product and if the investigator judges that dose pausation is required. These treatment pauses are allowed to an accumulated maximum of 4 weeks. Due to the long half-life of glepaglutide and the potential, longer persistence of the PD effects, it is considered appropriate to treat all AEs with an onset after the first dose of investigational product as treatment-emergent, including AEs with an onset during a treatment pauses. To ensure a consistent approach for the calculation of adverse event rates, treatment pauses are ignored both in the numerator (i.e. including AEs with an onset during treatment pauses) and in the denominator (i.e. including the entire observation period, regardless of any treatment pauses inbetween). Hence, patient-years of observation (PYO) will be calculated as [end of trial date – date of first trial dose + 1] / 365.25, where the 1 day is added to account for the first day of exposure to investigational product.

Note: the end of trial date is the Date of Disposition Event from the CRF Trial Completion Status form.

Exposure will be summarized by number of patients exposed and patient-years of observation.

Treatment interruptions will be defined as either 1) missing entries in the patient's eDiary because patient forgot to administer drug or forgot to record the dosing data or 2) treatment pauses agreed with the investigator as per protocol and reported as such in the eDiary.

Treatment interruptions will be summarized by number of patients with at least one treatment interruption, patient years of treatment interruptions, due to treatment pauses or due to missing data entry (because patient forgot to administer drug or forgot to record the dosing data), average duration of treatment interruptions (weeks) and by categories of cumulative duration of treatment interruptions.

Treatment pauses will be summarized by number of patients with at least one treatment pause, patient years of treatment pauses, average duration of treatment pauses (weeks) and by categories of cumulative duration of treatment pauses.

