7.2. ADVERSE EVENTS

Adverse events (AEs) will be coded using MedDRA V24.1. All treatment-emergent AEs (TEAEs) from the start of trial drug dosing will be collected.

Treatment-emergent AEs are defined as AEs with onset date on or after the first day of exposure to investigational product. Unless otherwise stated, all outputs will be presented for treatment-emergent AEs and, for simplicity, referred to as AEs.

Related AEs are defined as events classified as 'possibly related' or 'probably related' by the investigator.

Severity categories will include mild, moderate, and severe. Any missing severity will be imputed as severe prior to selecting the report that will contribute to the summary. As a result, a patient would be counted as severe due to a missing severity, even if the patient reported similar events at a lesser degree of severity. The same logic will be applied to the related AEs.

For patients who permanently discontinued treatment due to an AE and who also withdrawal trial prematurely, the AE leading to treatment discontinuation is counted as an AE leading to trial withdrawal (regardless of the cause marked as leading to trial withdrawal).

Common AEs are defined as events (preferred terms) occurring in \geq 5% of patients in the glepaglutide 10 mg OW or glepaglutide 10 mg TW treatment groups.

For all AE tables summarized by SOC and PT, a patient contributes only once to the count for a given AE on the SOC level and on the PT level within SOC. AE incidence tables will be sorted by descending frequency counts in hierarchical order of glepaglutide 10 mg twice weekly, then by glepaglutide 10 mg once weekly, and then by placebo. PTs will be sorted in similar hierarchical fashion within the SOC.

If there are less than 5 AEs of a type (AEs leading to treatment discontinuation, AEs leading to trial withdrawal, AESIs or AEs in other safety areas of interest) in the entire observation period, then only a listing will be prepared.

The following AE summaries will be presented by treatment group and will present the following information:

- n: number of patients experiencing at least one AE
- %: percentage of patients experiencing at least one AE
- E: number of AEs
- R: event rate (calculated as the number of AEs divided by PYO multiplied by 100)

An overall summary table will include the number and percentage of

- All adverse events
- Serious adverse events

25 August 2022

- Severity (Mild, Moderate, Severe, Missing)

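### The SAP gives treatment-emergent adverse events a start but no end, an undeclared departure from the protocol that lets events beginning after the Extension Trial starts count in the original arm

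*SAP*

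**What the plan says.** Protocol section 12.4 defines the treatment-emergent window at both ends. It opens on the first day of exposure to randomized treatment and runs "up through the last day prior to the start day of the Extension Trial or to the Week 28", the Week 28 limit applying to patients who do not enter the Extension.

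The SAP states only the opening. Section 7.2 reads: "Treatment-emergent AEs are defined as AEs with onset date on or after the first day of exposure to investigational product". Section 7.1 takes the same line: "it is considered appropriate to treat all AEs with an onset after the first dose of investigational product as treatment-emergent". Its reasons are the long half-life, the possible persistence of pharmacodynamic effects, and the wish to count events that begin during treatment pauses.

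For the denominator, SAP 7.1 ends patient-years of observation (PYO) at the end of trial and notes that "the end of trial date is the Date of Disposition Event from the CRF Trial Completion Status form". SAP 7.2 uses the end of trial date again to censor patients without the event in the time-to-event plots for selected events.

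The list of changes from the protocol in SAP section 8 has one row citing protocol 12.4, and it concerns the naming of the analyte. Protocol 12.1 says that the SAP will contain any modifications to the protocol's analysis plan and "thus serves as the overriding document dictating the statistical analyses to be performed".

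**The concern.** The end date in the protocol matters because exposure changes when it is reached. Protocol 6.2 and SAP 2.5 make patients from all three arms eligible for the Extension, where they receive glepaglutide. For a former placebo patient, an event that begins after the switch is no longer a placebo event. Under the SAP wording it would still be treatment-emergent and would be tabulated under placebo. SAP 4.2 analyzes patients as treated, but it has no rule for dividing a patient's follow-up at the Extension start.

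At stake are the adverse-event incidences, the event rates per 100 patient-years and the risk differences with 95% confidence intervals in SAP 7.2. The risk differences cover serious events, events of special interest, events leading to discontinuation or withdrawal, the other safety areas of interest and common events. For an event that glepaglutide makes more frequent, moving post-switch events into placebo narrows the difference from the active arms.

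**Working it through.** **1. Is there an end bound elsewhere in the SAP?**

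| Quantity | End point stated | Where |
|---|---|---|
| Treatment-emergent window, protocol | Day before Extension start, or Week 28 | Protocol 12.4 |
| Treatment-emergent window, SAP | None | SAP 7.1, 7.2 |
| PYO | Disposition date | SAP 7.1 |
| Censoring in time-to-event plots | End of trial date | SAP 7.2 |
| Counts, percentages, rate numerators, risk differences | None | SAP 7.2 |

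The event rate is the number of events divided by PYO, times 100. Its denominator has a stop date and its numerator has none.

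**2. Do the SAP's reasons cover the change?** Half-life, persistence of effect and pauses justify counting events after dosing stops or is interrupted. They do not bear on a patient who starts a new exposure in another trial.

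**3. Can a post-switch event reach this trial's data?** The documents show two possible routes.
- Exit interview. For Extension entrants, protocol 6.4 defines completion by "Patient completed EOT visit and exit interview, if consented". Protocol 10.4.10 says that the interviews "will be conducted no longer than 7 days after EOT visit" and has the investigator review the transcript for potential adverse events.
- Serious events. Protocol 11.4.2 requires reporting of those notified up to 30 days after the last dose of trial product.

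**4. Size: ceilings only.** Neither document gives an affected-event count or the timing of the first Extension dose. Assume that all 36 planned placebo patients (protocol 7.1) enter the Extension and receive glepaglutide on Day 169.
- Person-time to Day 169: 36 × 169 / 365.25 = 16.7 patient-years.
- Interview route, 7 days: 36 × 7 / 365.25 = 0.69 patient-years; 7 / 169 = 4.1%.
- Serious-event route, 30 days counted from Day 169: 36 × 30 / 365.25 = 2.96 patient-years; 30 / 169 = 17.8%. It is less if the last dose was earlier.

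These are shares of person-time, not estimates of bias. To turn them into rates, let r be the event rate after the switch relative to before, with every event over the added s days captured. The range r = 1 to 3 is an assumption. If PYO stops at Day 169 and the numerator does not, the placebo rate rises by r × s / 169. If PYO runs on through the added days, the rise is (169 + r × s) / (169 + s) − 1.

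| Route | r | PYO stops at Day 169 | PYO runs on |
|---|---|---|---|
| 7 days | 1 | 4.1% | 0% |
| 7 days | 3 | 12.4% | 8.0% |
| 30 days, serious events only | 1 | 17.8% | 0% |
| 30 days, serious events only | 3 | 53.3% | 30.2% |

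For incidence, one additional affected placebo patient is 1 / 36 = 2.8 percentage points. This applies only if that patient had not already had the same preferred term, since SAP 7.2 counts a patient once per term.

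**5. With the protocol's bound restored,** the spill-over is 0 days by definition. No figure stated in either document changes.

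**The case against.** The strongest reply is that the SAP already implies a bound. Section 7.1 asks for a consistent approach to numerator and denominator, and both 7.1 and 7.2 speak of an entire observation period, which for PYO closes at the end of trial date. Extension entrants also have their final visit at Visit 10 (protocol Table 1, footnote 19) and complete the end-of-trial form there (protocol 10.4.10). Later events would ordinarily fall to the Extension Trial's own database. Exit interviews cover a consenting subset in five countries, and nothing says that an event which began under the Extension would be entered in this trial. The serious-event route would not carry non-serious injection-site or abdominal complaints.

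Most of this stands as an argument about size. It does not supply the missing rule. The consistency statement in SAP 7.1 concerns treatment pauses, and no sentence limits which events enter the counts. Even an implied bound at the disposition date would not be the protocol's bound. Protocol 6.4 ties completion to the interview where consented, while 10.4.10 places the end-of-trial form at Visit 10, so the disposition date is itself ambiguous relative to the Extension start.

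A reader might infer more: that early reactions to a first glepaglutide dose will be attributed to placebo, and that time-to-first-event comparisons will shrink. The documents do not support either. They show that such events can be counted, not that any will be. SAP 7.2 also says that the time-to-event outputs are visual displays, not for inference or comparison between arms.

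**Conclusion.** The point holds as a departure from the protocol that SAP section 8 does not declare. The SAP's definition lacks the protocol's end date, the SAP governs, and an event with onset on or after the Extension start that reaches this trial's data can be counted in the patient's original arm. The gap applies to all arms. It matters most for placebo, because that is where exposure changes from none to glepaglutide.

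The practical effect is probably small and cannot be computed, because the documents give neither the timing of the first Extension dose nor the number of patients interviewed. The 4.1% and 17.8% shares are ceilings that need every placebo patient to switch on Day 169 and to be observed for the full 7 or 30 days. The rate increases rest further on assumed post-switch rate ratios.

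Any bias would fall on descriptive safety results. The risk differences carry no formal hypothesis test, and no efficacy or confirmatory conclusion is affected. The point still merits correction, because the remedy is nearly free and these tables carry the safety comparison with placebo.

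**What to change.** Restore the protocol's end bound in SAP 7.2: onset from the first dose through the last day before the Extension Trial start day, or through Week 28 for patients who do not enter the Extension. Align SAP 7.1 with it. Use the Extension Trial start day, as the protocol does, and not the first Extension dose; the documents do not show that these are the same date.

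Apply the same cut-off to adverse-event counts, PYO, and censoring in the time-to-event plots. Events with later onset can be listed separately. If the sponsor prefers the open-ended definition, declare it in SAP section 8 and justify it for patients who move to glepaglutide.

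The cost is one or two sentences in the SAP and a date cut in the adverse-event and exposure programs. No new data are needed beyond the Extension start date for each entrant.

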- Relationship (Possibly, Probably, Unlikely, Not Related, Missing)
- AEs leading to trial withdrawal
- AEs leading to treatment discontinuation
- AEs leading to treatment pause
- Outcome (Recovered/Resolved, Recovering/Resolving, Recovered/Resolved with Sequelae, Not Recovered/Not Resolved, Fatal, Unknown, Missing)

Additional AE tables will include:

- AEs by System Organ Class (SOC) and Preferred Term (PT)
- AEs Occurring in >=5% of Patients Treated with Glepaglutide by SOC and PT
- Summary of Serious AEs
- Serious AEs by SOC and PT
- Related AEs by SOC and PT
- Severe AEs by SOC and PT
- Moderate AEs by SOC and PT
- Mild AEs by SOC and PT
- AEs of Special Interest (AESIs) by Type and PT
- Other safety areas of interest (see Table 8) by SOC and PT

Other safety areas of interest are defined based on:

- their relevance for the SBS population or known class effects with other glucagon-like peptide-2 (GLP-2) receptor agonists (RAs) (e.g. gastrointestinal stenosis and intestinal obstruction [including stoma complications]; fluid retention and volume overload; hepatic disorders)
- general applicability to injectable peptide drugs (e.g. injection site reactions; hypersensitivity reactions)
- general interest for any new drug administered long-term (e.g. rare events; adverse event by organ system or syndrome [e.g., cardiac, renal and hepatic events]).

For these other safety areas of interest, events will be captured by applying the MedDRA queries as defined in Table 8. Both overall summary tables and tables by PT will be presented by treatment group for each safety area of interest separately. The following plots will be presented for injection site reactions and abdominal pain:

• Survival probability function plots (one minus the Kaplan-Meier estimator) for the time to the first occurrence of the selected AEs will be presented. Time to the first AE will be calculated from the date of first dose of investigational product.

• Mean cumulative function plots to evaluate recurrent AEs occurring after the date of the first dose of investigational product, showing the mean number of events over time.

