Patients that do not experience the 'event' will be censored at the patient end of trial date. The purpose of these outputs will be to provide a visual presentation of the occurrence over time of these AEs after the first dose of investigation product, rather than any inference or comparison across the treatment groups. AEs with missing (or partially missing) onset date will not be included in these type outputs with a clear statement in a footnote if applicable.

Point prevalence plots with the proportion of patients with events over time will be presented for abdominal pain. The denominator at a specific time point will be the number of patients at risk.

Safety area of interest	Methodology
Gastrointestinal stenosis and intestinal obstruction (including stoma complications)	SMQ 'Gastrointestinal obstruction' (narrow scope) combined with HLT 'Stoma complications' (all terms)
Gallbladder and biliary disease	SMQ 'Biliary tract disorders' (narrow scope) combined with HLT 'Cholecystitis and cholelithiasis' (all terms)
Fluid retention and fluid overload	SMQ 'Haemodynamic oedema, effusions and fluid overload' (narrow scope)
Abdominal pain	HLT 'Gastrointestinal and abdominal pains (excl oral and throat)' (all terms)
Hypersensitivity reactions	SMQ 'Hypersensitivity' (broad scope)
Injection site reactions	Tick mark for 'study treatment injection site reaction' in eCRF (AE form)
Cardiac adverse events	SMQ 'Cardiac arrhythmias' (narrow scope) combined with SMQ 'Cardiac failure' (narrow scope)
Renal adverse events	SMQ 'Acute renal failure' (broad scope)
Hepatic adverse events	SMQ 'Hepatic disorders' (broad scope)
Rare events	CMQ based on EMA Designated Medical Event list, 2020 ¹

Table 8 Methodology for capture of adverse events relevant for other safety areas of interest

¹ https://www.ema.europa.eu/en/documents/other/designated-medical-event-dme-list_en.xlsx **Abbreviations**: CMQ: customized MedDRA query; EMA: European Medicines Agency; HLT: higher level term; MedDRA: Medical Dictionary for Regulatory Activities; SMQ: standardized MedDRA query

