The risk difference with 95% confidence intervals (using the Miettinen and Nurminen estimation method) will be estimated to quantify the uncertainty of the treatment comparison between placebo and glepaglutide 10 mg OW, placebo and glepaglutide 10 mg TW, and placebo and either of the glepaglutide groups (glepaglutide total); no formal hypothesis testing will be performed. This comparative analysis will be done for AEs leading to treatment discontinuation, AEs leading to trial withdrawal, SAEs, prespecified AESIs, other safety areas of interest and AEs occurring in \geq =5% of patients treated with glepaglutide (10 mg once weekly or 10 mg twice)

weekly). The result will be presented graphically with a dot plot in the left panel illustrating the event rates by treatment group (e.g., glepaglutide 10 mg once weekly and placebo) and a forest plot in the right panel presenting the corresponding risk difference and confidence intervals.

As a separate table, Symptoms of Injection Site Reactions will be presented with patient counts, percentages, number of events, and adverse event rate for injection site reactions including spontaneous pain, pain on palpitation, itching, redness, oedema, induration/infiltration, and other. The above symptoms are captured for AEs with a Tick mark for 'study treatment injection site reaction' in the eCRF (AE form).

The following patient listings will be provided as tables:

- Deaths
- Serious AEs
- AEs Leading to Trial Withdrawal
- AEs Leading to Treatment Discontinuation
- AEs Leading to Treatment Pause
- AESIs
- AESIs Details on Neoplasms
- Other Important Events

A listing of all TEAEs will be provided.

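### The SAP drops the protocol's time-to-event analysis for each AESI without recording it, and its fewer-than-5-events rule conflicts with the risk differences it plans for AESIs

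*SAP*

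**What the plan says.** **Time-to-event analysis.** Protocol 11.4.1.2 names four AESIs: neoplasms, suspicion of liver injury, pancreatitis and cholecystitis. Protocol 12.4 commits to more than descriptive tables for them: "for each AESI, a time to event analysis will be performed", with details left to the SAP. In SAP 7.2 the time-to-first-event output is limited: "The following plots will be presented for injection site reactions and abdominal pain". Neither is an AESI. The SAP adds that these outputs show occurrence over time "rather than any inference or comparison across the treatment groups". SAP section 8 (changes from protocol) has one entry against protocol 12.4, on PK nomenclature. Under protocol 12.1 the SAP overrides the protocol's analysis text.

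**Between-arm estimate.** SAP 7.2 plans risk differences with Miettinen-Nurminen 95% intervals for once weekly, twice weekly and total glepaglutide, each against placebo. On scope it says: "This comparative analysis will be done for AEs leading to treatment discontinuation, AEs leading to trial withdrawal, SAEs, prespecified AESIs", and it goes on to include the other safety areas of interest and AEs in at least 5% of glepaglutide-treated patients.

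**Sparse-event rule.** The same section sets a threshold of fewer than 5 events of a type. It applies to four categories: events that end treatment, events that end trial participation, AESIs, and the Table 8 areas. The rule closes with these words: "withdrawal, AESIs or AEs in other safety areas of interest) in the entire observation period, then only a listing will be prepared".

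**The concern.** There are two separate problems.

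The first is traceability. An analysis promised for the four harms named in advance is absent from the overriding document. The table that should tell a reader so is silent.

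The second is a conflict inside SAP 7.2. One paragraph plans an interval for each prespecified AESI. Another names AESIs and allows only a listing when events are few. Read naturally, 'only' cancels the AESI-level by-arm table and the risk difference. The rule counts events over all arms rather than patients, so five recurrences in one patient earn a table while four affected patients in one arm do not. 'Type' is undefined.

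What is at stake is whether the report gives, for each named harm, a by-arm count with a denominator and a stated uncertainty. That includes the upper limit that belongs with a zero count.

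**Working it through.** **Inputs from the documents.** About 108 patients, 36 per arm (protocol 7.1). Threshold: fewer than 5 events of a type over the whole observation period (SAP 7.2). Method: Miettinen-Nurminen 95% interval (SAP 7.2).

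**Input not in the documents.** Neither document gives an expected AESI rate or a safety precision target. The risks below are assumptions, shown as a range.

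**The plan's own figure.** The only computed figure at 108 patients is the efficacy power. SE = 2.62 × √(2/36) = 0.6175; the standardised effects are 2.2/0.6175 = 3.56 and 2.0/0.6175 = 3.24; the two-sided 0.025 critical value is 2.241; the two tests correlate 0.5 through the shared placebo arm. Power for at least one success is 95.8% (stated: 95%), and 91.4% in the less favourable scenario (stated: 91%). This confirms the sample size basis and says nothing about safety.

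**Chance of a listing only, each AESI its own type.** With one event per affected patient, P(X ≤ 4) for X ~ Binomial(108, p):

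| Assumed pooled risk | Expected events | P(listing only) |
|---|---|---|
| 1% | 1.08 | 99.5% |
| 2% | 2.16 | 93% |
| 3% | 3.24 | 78% |
| 4% | 4.32 | 57% |
| 5% | 5.40 | 37% |
| 6% | 6.48 | 22% |
| 8% | 8.64 | 6% |
| 10% | 10.8 | 1.4% |

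The chance is 50% at a pooled risk of 4.3%. With unequal arms, 10% on twice weekly and 1% in the other two, the sum Binomial(36, 0.10) + Binomial(72, 0.01) gives P(≤ 4) = 56%. Repeat events in one patient would lower all these figures, because the rule counts events.

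**All four AESIs pooled as one type.** With a Poisson mean of 4 × 108 × r:
- r = 1% each: mean 4.32, P(≤ 4) = 57%.
- r = 2% each: mean 8.64, P(≤ 4) = 7%.

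**What the planned interval would show below the threshold.**

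| Split (active v placebo) | Difference, points | Miettinen-Nurminen 95% CI |
|---|---|---|
| 4/36 v 0/36 | 11.1 | 0.8 to 25.4 |
| 3/36 v 0/36 | 8.3 | −1.8 to 21.9 |
| 2/36 v 0/36 | 5.6 | −4.5 to 18.3 |
| 4/72 v 0/36 | 5.6 | −4.4 to 13.5 |
| 0/36 v 0/36 | 0 | −9.8 to 9.8 |

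For the last row, the limit d solves d/(1 − d) = 1.96² × 72/(71 × 36) = 0.108, so d = 0.098. The method works at every count under the threshold, and one such split has an interval that excludes zero.

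**Routes that escape the rule.** The rule does not name SAEs or common AEs. SAP 7.2 defines common AEs as preferred terms in at least 5% of the once-weekly or the twice-weekly group. Since 2/36 = 5.6%, two patients in one glepaglutide group with the same preferred term qualify, and 4/36 = 11.1% clearly does.

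**The case against.** The strongest reply is that a reader might infer that the named harms will usually get no between-arm estimate, and the documents do not support that.

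- **The risk difference is planned.** It is lost only if the count falls below 5 and the rule prevails. Even then, serious cases, or cases sharing a common preferred term, keep an interval by another route. The AE and SAE tables by system organ class and preferred term remain, by arm.
- **Neighbouring outputs exist.** The gallbladder/biliary and hepatic areas in SAP Table 8 are broader than the matching AESIs and reach 5 events more easily. Liver enzymes also have shift tables and individual trajectories. Listings are sorted by treatment group, so at most four events can be counted by hand.
- **The missing time-to-event analysis removes no contrast.** The protocol names no comparison for it and bars inferential safety tests. The SAP's own plots are declared non-comparative.
- **The rates are assumed**, and the pooled reading of 'type' gives much lower chances of a listing.
- **Listing very sparse events is a legitimate choice**, and the SAP may modify the protocol's analyses.

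All of this stands as a limit on size. It leaves three things untouched: the conflict within SAP 7.2, the undefined 'type', and the unrecorded removal. Preferred-term tables also do not replace an AESI-level estimate, because one AESI can be spread over several terms. SAP 7.2 itself plans a table of AESIs by type and preferred term, which favours reading each AESI as a type.

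**Conclusion.** The point holds in limited form. The unrecorded loss of the AESI time-to-event analysis is a matter of record and depends on no assumption. It costs a display of timing and the audit trail, not a treatment comparison.

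The sparse-event rule conflicts with the planned AESI risk differences. If each AESI is a type, with one event per affected patient, a listing only is more likely than not when the pooled risk is below about 4.3%. If the AESIs are pooled, the chance is 57% at 1% each and 7% at 2% each. The affected quantity is the AESI-level by-arm count and interval, mainly for non-serious cases spread over several preferred terms. In that situation a 4/36 v 0/36 split (11.1 points, 95% CI 0.8 to 25.4) could go unreported. It should not be read as certain to be lost, since serious cases or a shared preferred term would bring an interval back.

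The point does not extend to every safety area. Protocol 4.3.2 reports abdominal pain, stoma complication and peripheral edema each in more than 20% of phase 2 patients. At rates of that order the rule would hardly ever apply. Suspicion of liver injury could fall either way.

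**What to change.** In SAP 7.2:

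1. Exempt the four AESIs from the fewer-than-5 rule. For each, report n/N and % by arm and the already planned risk difference with its 95% interval whatever the count, including zero.
2. Define 'type' as each AESI or safety area taken separately. Count patients rather than events for any threshold that remains.
3. Restore a time-to-first-event display for each AESI, using the code planned for injection site reactions and abdominal pain. Otherwise, record its removal with a reason in SAP section 8.

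Exempting every Table 8 area is not needed. The cost is SAP wording and a few extra outputs from existing programs, with no new data. The downside is some sparse tables and plots with wide intervals.
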